6.3. Missing Data

For safety analysis missing data will not be estimated and/or imputed in any way. All subjects who withdraw prematurely from the study will be documented and the reason for withdrawal will be reported in the Clinical investigation report. All available data from subjects who withdraw will be listed and all available planned data will be included in the summaries according to analysis data sets.

In case of an AE/ ADE with partial/ missing start/ stop dates, the rules outlined in Section 9.3 will be applied.

Subjects with missing NLF-SRS grades at Baseline and/or at Week 24 will be considered as non-responders for the primary analysis. Since it is very unlikely that the assessment of only one NLF will be missing, presumably either no or both assessments will be available for one subject at a certain time point. Therefore, this imputation method will probably decrease the response rate in both treatment groups simultaneously. Due to the fact that the sample size calculation was based on rather high response rates (88% for Juvéderm® Ultra XC and 87% for Princess® FILLER Lidocaine), lower response rates will make it more difficult to demonstrate non-inferiority of Princess® FILLER Lidocaine and thus this approach is considered to be conservative. In addition to this approach, a complete case analysis (using the available data without any imputation), a best-case analysis (missing values for Princess® FILLER Lidocaine will be considered as a response, missing values for Juvéderm® Ultra XC will be considered as a non-response), a worst-case analysis (missing values for Princess® FILLER Lidocaine will be considered as a non-response, missing values for Juvéderm® Ultra XC will be considered as a response), and a tipping point analysis will be conducted as sensitivity analyses.

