- Safety reasons including abnormal and clinically significant changes in visual examinations (see Section 10.8.4)
- Treating investigator's decision
- Poor compliance and/or disregard of the treating investigator's instructions
- Major CIP violation

In case of early withdrawal, reasons, circumstances and findings should be described as completely as possible on the "Early Termination" page in the CRF respecting the subject's privacy. Subjects who are withdrawn prematurely should undergo an early termination visit with the assessments that are scheduled for Week 40 (Visit 8a) or Week 52 (Visit 8b) or Visit 8c.

In accordance with similar studies in this indication, the expected lost to follow-up rate is estimated to reach approximately 5% and repeat treatments will be offered in this clinical investigation to further decrease the amount of lost to follow-up subjects. Due to the split face design, minimal attrition bias is expected.

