9.4 Subject Enrollment, Number and Duration of Subject's Participation

Subjects who have signed the informed consent form (ICF) and comply with all inclusion and exclusion criteria will be enrolled, and undergo treatment at Visit 2 on Day 0. Screening and Baseline may be combined in one visit. If full correction is not achieved after the initial treatment, subjects may receive a touch up treatment 2 weeks later and can receive repeat-treatment (with Princess® Filler Lidocaine only) at Week 36 (Visit 6) or Week 48 (Visit 7) or Visit 7c. Each subject is expected to be in the clinical investigation for a maximum of 104 weeks including the temporary hold on repeat-treatment.

CPH-301-201200F

Approximately 300 subjects will be screened in the USA; the enrollment of a total of approximately 270 subjects is planned in order to obtain at least 240 evaluable subjects randomized in an 1:1 ratio to each clinical investigation group (accounting for a screening failure rate of approximately 10%, as well as approximately 10% of subjects to be excluded from the Per-Protocol Set due to major protocol deviations or subjects lost to follow-up).

The clinical investigation is planned to be conducted at approximately 10-12 US sites with enrolment target of 23-27 subjects per site. Competitive recruitment may be allowed to stimulate enrollment, but no site will be allowed to enroll more than 54 subjects (20%) unless prior approval of the sponsor is given; in this case, the maximum number of subjects per site is capped at 68 (25%). This will maintain adequate balance between the investigational sites.

10

Clinical investigation Procedures and Assessments

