10.13 Time-Windows

A time deviation of \pm 5 days is allowed for each visit, except for phone contacts (+/- 24 hours) and for the touch-up visit at Week 2 (+/- 3 days). Clinical investigational sites must adhere to the Schedule of Clinical investigation Procedures and Assessments (see Section 2.1) and visit windows, and subjects must ensure they are available for those visits. However, if for practical reasons, e.g. bank holidays, a visit window cannot be met, a visit can be scheduled as close as possible to that visit window. However, any deviation from the visit schedule and its associated time windows will still be documented as a protocol deviation.

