In order to assess the homogeneity of the primary effectiveness outcome measure and of the treatment effect among the clinical investigational sites, a mixed logistic regression model with treatment, site, and treatment-by-site interaction as fixed effects and random subject effects will be fitted. Small clinical investigational sites with less than ten subjects will be pooled and a two-sided alpha level of 15% will be used to test for a treatment-by-site interaction. In case that the treatment-by-site interaction is not statistically significant (at the alpha level mentioned above), the treatment-by-site interaction will be removed from the mixed model and the confidence interval for the difference in proportions will be derived from this mixed model adjusted for site effects. If the treatment-by-site interaction effect is statistically significant (at the alpha level mentioned above), the treatment difference is not interpretable in the model. In this case, the treatment difference in the main effect model without adding the interaction effect is tested and in addition, the treatment difference by site will be presented and observed heterogeneities will be evaluated.

Subjects with missing NLF-SRS grades at Baseline and/or at Week 24 will be considered as non-responders for the primary analysis. Since it is very unlikely that the assessment of only one NLF will be missing, presumably either no or both assessments will be available for one subject at a certain time point. Therefore, this imputation method will probably decrease the response rate in both treatment groups simultaneously. Due to the fact that the sample size calculation was based on rather high response rates (88% for Juvederm® Ultra XC and 87% for Princess® FILLER Lidocaine), lower response rates will make it more difficult to demonstrate

non-inferiority of Princess® FILLER Lidocaine and thus this approach is considered to be conservative. In addition to this approach, a complete case analysis (using the available data without any imputation), a best-case analysis (missing values for Princess® FILLER Lidocaine will be considered as a response, missing values for Juvéderm® Ultra XC will be considered as a non-response), a worst-case analysis (missing values for Princess® FILLER Lidocaine will be considered as a non-response, missing values for Juvéderm® Ultra XC will be considered as a response), and a tipping point analysis will be conducted as sensitivity analyses.

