4.3. Per-Protocol Set

The Per-Protocol Set (PPS) is defined as a subset of the subjects in the FAS who had no major protocol deviations upto Week 24. Subjects with randomization errors will be considered as major protocol deviations and excluded from PPS.

The PPS will be used for effectiveness analysis.

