4.5. Protocol Deviation and Non-Compliances

Non-compliances are unplanned deviations from applicable regulations, guidelines, other standards, controlled documents, contractual agreements, and/or protocol or project specific requirements. Any change, divergence, or departure from the study design or procedures defined in the protocol; a subset of non-compliances occurring at an individual subject level, or deviations that are related to COVID-19 are defined as protocol deviations (PDs).

All subjects who comply with criteria for inclusion into FAS, PPS and SAF, as defined in section 4, will be included in respective analyses.

Protocol deviations will be identified (in a blind manner) and discussed throughout the study. Prior to database lock, all protocol deviations will be listed in a blinded manner. Their relevance (minor / major) and their impact on the effectiveness assessments, i.e., with respect to exclusion of subjects from PPS and/or FAS will be evaluated in the Blind Data Review Meeting (BDRM). Possible major protocol deviations may include but are not limited to deviations related to premature termination, the inclusion and exclusion criteria, and prohibited concomitant treatments.

For the preparation of the BDRM, subject listings will be generated with all protocol deviations and non-compliances identified from eCRF entries and from monitoring documentation system. These listings

This document is confidential.

will be reviewed by Croma Pharma and SH study team. The final decision with regards to protocol deviations and populations will be taken in the BDRM.

The number and percentage of subjects with a protocol deviation by type of deviation category will be presented by treatment group. In addition, protocol deviations related to COVID-19 will be summarized in a similar fashion.

All protocol deviations will be provided in a by-subject listing with the categorization of minor or major. Protocol deviations related to COVID-19 will be listed separately.

Primary reasons and categories of the PDs at individual subject levels are:

- Concomitant Medication
- Dosing
- Enrollment Criteria
- Informed Consent
- Laboratory
- Non-compliance
- Other
- Regulatory
- Visit Schedule
- Visit/Procedure Required

This document is confidential.

5. Estimands

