5.1. Primary Effectiveness Endpoint

The estimand for the primary effectiveness endpoint is defined as follows:

- Treatment: Princess® FILLER Lidocaine and Juvéderm® Ultra XC for the treatment of NLF (both sides) in each subject.
- Population: Of all subjects defined by the study inclusion / exclusion criteria, the analysis population will include subjects who were randomized to the study treatment and received both treatments (Princess® FILLER Lidocaine and the control medical device) as initial treatment at the same visit (FAS population).
- Variable: A binary variable indicating the subject is alive and has a NLF-SRS response based on the independent blinded evaluating investigator live assessment using the NLF-SRS at Week 24 after initial treatment and relative to baseline assessments. NLF-SRS responder with regards to each specific NLF is defined as a subject with at least one grade improvement from baseline in NLF-SRS in that NLF.
- Intercurrent events:
 - The intercurrent event 'death' is very unlikely in this study, however, in case of death prior to Week 24, this will be considered as non-response following the composite strategy.
 - Major protocol deviations impacting the NLF-SRS assessment will be handled using the treatment-policy strategy, i.e., the NLF-SRS value at Week 24 will be used for categorization of response.
- Population-level summary: Paired difference of NLF-SRS response rates between Princess® FILLER Lidocaine and the control medical device for non-inferiority comparison.

Study discontinuation (due to any reason) prior to Week 24 is not considered as an intercurrent event, however this will lead to missing Week 24 values, which will be imputed using single imputation strategy as non-response for the primary analysis of this estimand. Subjects with missing NLF-SRS value at Baseline will be considered as non-response for the primary analysis of this estimand.

5.2. Key Secondary Effectiveness Endpoint 1

The estimand for the key secondary effectiveness endpoint 1 is defined as follows:

- Treatment: Princess® FILLER Lidocaine and Juvéderm® Ultra XC for the treatment of NLF (both sides) in each subject.
- Population: Of all subjects defined by the study inclusion / exclusion criteria, the analysis population will include subjects who were randomized to the study treatment and received both treatments (Princess® FILLER Lidocaine and the control medical device) as initial treatment at the same visit (FAS population).

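### Scoring ungraded subjects as non-responders on both folds makes the FAS non-inferiority test easier to pass, not harder, and no rule requires those subjects to leave the PPS

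*SAP*

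**What the plan says.** **The rule.** SAP 5.1 states that discontinuation before Week 24 is not an intercurrent event. It leaves missing Week 24 values, "which will be imputed using single imputation strategy as non-response for the primary analysis of this estimand". SAP 6.3 applies the same scoring to a missing Baseline grade.

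**The rationale.** SAP 6.3 and Protocol 14.2 both expect the two folds of a subject to be missing together. Protocol 14.2 says: "Therefore, this imputation method will probably decrease the response rate in both treatment groups simultaneously". Both then argue that "lower response rates will make it more difficult to demonstrate non-inferiority of Princess® FILLER Lidocaine and thus this approach is considered to be conservative".

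**The decision.** Protocol 14.2 and SAP 8 require the FAS and the PPS both to support non-inferiority. SAP 8.2.1 repeats the same analysis on the PPS. No sensitivity or supportive analysis enters the decision.

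**Who is in the PPS.** SAP 4.3 has the PPS "defined as a subset of the subjects in the FAS who had no major protocol deviations upto Week 24" and does not mention a Week 24 grade. SAP 4.5 lists premature termination only as a possible major deviation and leaves classification to the blind data review. Under Protocol 10.13, "any deviation from the visit schedule and its associated time windows will still be documented as a protocol deviation", but nothing makes a missed visit major. The intent that lost subjects leave the PPS appears only in the accrual arithmetic of the synopsis and Protocol 9.4: "approximately 10% of subjects to be excluded from the Per-Protocol Set due to major protocol deviations or subjects lost to follow-up".

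**The concern.** In a non-inferiority trial, bias toward no difference is the unsafe direction. The rationale treats two situations as one. If response rates were truly lower and the folds behaved independently, discordance would rise and the test would become harder. Imputing both folds of the same subject as non-response adds no discordance at all; it dilutes both the difference and its variance. Because SAP 5.1 treats discontinuation as missing data, the dilution is bias and not part of the estimand.

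At stake is whether the joint FAS and PPS decision keeps its nominal error. That depends on case-by-case classification at the blind review. The SAP also sends mixed signals: SAP 8.4 and 8.5 plan best-case, worst-case, multiple-imputation and complete-case analyses on the PPS, which presumes ungraded subjects may be in it, while the opening of SAP 8 places best- and worst-case on the FAS.

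**Working it through.** **Inputs.** Margin -10% and one-sided alpha 0.025 (SAP 8.2.1); response 88% and 87% with independent folds (SAP 2.7); 270 randomized (SAP 2.6). For the missing fraction m, Protocol 9.3 says "the expected lost to follow-up rate is estimated to reach approximately 5" per cent, with no time point, so Week 24 missingness may be lower. Assumptions: missingness unrelated to outcome; a further 5% of graded subjects excluded from the PPS at random (the plan's 10% minus 5%); a paired Wald limit.

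**The plan's own figure.** The discordant share is 0.87 × 0.12 + 0.88 × 0.13 = 0.2188. Simulating 222 subjects with the Newcombe-Wilson limit at one-sided 0.05 gives 88.6% power, against the stated 90%. The plan used 1600 simulations (standard error about 0.75 point), so this is a reasonable match. At the SAP's 0.025 the same 222 subjects give 80.9%.

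**Mechanism.** Let d be the difference and ψ the discordant share among graded subjects. Adding a fraction m as non-response on both folds gives:

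- difference: (1-m)d
- discordance: (1-m)ψ
- lower limit: (1-m)d - z·√{[(1-m)ψ - (1-m)²d²]/N}

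This is close to (1-m) times the graded-only limit. Testing -10% in the FAS is therefore like testing -10%/(1-m) in graded subjects; at m = 5% that is -10%/0.95 = -10.5%.

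**Rationale against rule.** Power at 87% versus 88%, N = 270:

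| Situation | Discordance | Power |
|---|---|---|
| No missing data | 21.9% | 88.5% |
| Both rates truly × 0.95, independent folds | 28.1% | 80.2% |
| 5% imputed as non-response on both folds | 20.8% | 90.3% |

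The plan's argument describes the second row; its rule produces the third.

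**Worked example.** Suppose 14 of 270 subjects are ungraded. Among the 256 graded, 21 respond only on the test side and 33 only on the control side.

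- Graded only: d = -12/256 = -0.0469; SE = √[(54/256 - 0.0469²)/256] = 0.0286; lower limit -10.28% (fails).
- FAS with imputation: d = -12/270 = -0.0444; SE = √[(54/270 - 0.0444²)/270] = 0.0271; lower limit -9.75% (passes).

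If the 14 leave the PPS, the PPS gives the first result and the trial correctly fails. If they stay, both tests pass.

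**Error at a true -10 points** (78% versus 88%, independent folds, 1,000,000 simulated trials per cell; repeat runs agree within about 0.1 point):

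| Missing | Other PPS exclusions | FAS alone | Joint, all ungraded stay in PPS | Joint, half leave | Joint, all leave |
|---|---|---|---|---|---|
| 0% | none | 2.6% | 2.6% | 2.6% | 2.6% |
| 2.5% | 5% | 3.2% | 2.6% | 2.4% | 2.3% |
| 5% | none | 3.8% | 3.8% | 3.2% | 2.6% |
| 5% | 5% | 3.8% | 3.1% | 2.8% | 2.4% |

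The 2.6% in the first row is the Wald method's own error, so not all of each figure comes from this rule. With no missing data and 5% other exclusions, joint error is 2.1%.

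With within-subject correlation 0.3, 5% missing and 5% other exclusions, joint error is 3.5% (all stay) or 2.6% (all leave). At the protocol's one-sided 0.05, FAS error goes from 5.2% to 7.2% at 5% missing; joint error with 5% other exclusions is 5.9% or 4.8%.

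**The case against.** The sponsor can answer that the FAS never decides alone, that the accrual text already puts lost subjects outside the PPS, that premature termination is named as a possible major deviation, and that classification is blind, so it cannot be steered by treatment. On that reading the gap is confined to subjects who miss Week 24, do not terminate, and are rated minor. The effect at realistic inputs is small: 2.3% to 2.6% at 2.5% missing with other exclusions. If ungraded subjects would truly have failed on both folds, scoring them so is correct and causes no bias. The planned complete-case, worst-case and tipping-point analyses would reveal any dependence on the rule.

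Much of this stands. The intent is documented, the size is modest, and the all-stay column is the unfavourable end of the range. Three things are not answered. The stated direction of the bias is wrong whatever its size. Accrual arithmetic does not define an analysis set, and SAP 4.3 and 4.5 bind nobody to it. The sensitivity analyses can show a problem but cannot change the conclusion. Blind classification prevents steering by treatment, but it does not undo dilution toward zero.

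**Conclusion.** The concern holds. The imputation is not conservative for this paired non-inferiority test: at 5% missing it raises FAS error from 2.6% to 3.8%, and raises power from 88.5% to 90.3%. Joint error at 5% missing then lies between 2.6% and 3.8%, or between 2.4% and 3.1% with 5% other PPS exclusions, depending on a classification that the SAP leaves open. If the documented intent is followed, the consequence is small. If ungraded subjects stay in the PPS, nothing in the decision rule corrects it.

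The direction follows from algebra and is firm. The error rates rest on missingness unrelated to outcome, independent folds (except where correlation is stated), and a 5% missing fraction that the protocol gives without a time point. This should be fixed before the blind data review.

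**What to change.** 1. Delete the claim of conservatism from SAP 6.3 and record the correction to Protocol 14.2 in SAP 11.
2. State in SAP 4.3 that a subject without a Baseline or Week 24 NLF-SRS grade for the endpoint being tested is excluded from the PPS for that test. For key secondary endpoint 1 this means no median reviewer grade can be derived. Deaths before Week 24 stay as non-response in both sets, under the composite strategy of SAP 5.1.
3. Reconcile the opening of SAP 8 with 8.4, 8.5 and the PPS missing-data tables. Adjust the PPS counts in SAP 7.1 and the FAS-PPS comparison in 7.2, because PPS membership may differ by endpoint.

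An alternative to step 2 is to leave the PPS as it is and also require the planned FAS complete-case lower limit to exceed -10%. Its place in the testing hierarchy would have to be stated. At 5% missing with 5% other exclusions it gives error 2.4% and power 85.9%.

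Neither option corrects informative missingness; the worst-case and tipping-point analyses remain for that.

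**Cost.** Text edits plus revised tables and shells; no new data. Power at 87% versus 88% with 5% missing is 86.9% if ungraded subjects leave the PPS and 90.3% if they stay. With 5% other exclusions it is 84.8% against 87.9%. Against 88.5% with no missing data, the loss without other exclusions is 88.5 - 86.9 = 1.6 points; the rest of the gap is power created by the imputation.

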6.4. Visit Windows

There are no plans to derive visit windows; visits will be used in the analyses as reported on the electronic Case Report Form (eCRF).

This document is confidential.

7. Demographic, Other Baseline Characteristics and Medication

7.1. Subject Disposition and Withdrawals

The number of subjects in each of the 3 study populations (FAS, PPS, SAF) will be summarized; the number of subjects screened will also be summarized.

Screen-failure subjects (ie, subjects screened but not treated) and the associated reasons for screen failure will be tabulated overall for all screened subjects. The number and percentage of subjects who complete the study in the FAS will be tabulated. The reasons for withdrawal from the study as recorded on the termination pages of the eCRFs will be summarized with number and percentage. All subjects who withdrew during the study will be listed by discontinuation reason for the FAS.

7.2. Demographic and Other Baseline Characteristics

The following demographic data will be collected at Screening or baseline (Day 0/Visit 2):

- Age (years) = (Inform consent date - date of birth + 1) / 365.25 and truncated to complete years
- Sex (%)
- Race (%)
- Ethnicity (%)
- Fitzpatrick skin type (Type I ~ Type VI) (%)
- Body weight (kg)

Demographic data and baseline characteristics will be statistically described for subjects in the FAS and listed in the SAF by groups (i.e., Group A, Group B and the repeat-treatment subgroup). If difference between FAS & PPS is more than 5%, then demographic data and baseline characteristics will be statistically described for subjects in the FAS and PPS, respectively.

7.3. Medical/Aesthetic Procedures History

Medical/aesthetic procedures history will be collected at Screening, from subject interview and medical records (if available), covering relevant past medical history with particular reference to:

- Diseases and medical conditions addressed in exclusion criteria
- Previous aesthetic and surgical procedures in the treatment area
- All medications taken by the subject in the previous ten days (regularly or occasionally), including over-the-counter and herbal medicines, and with special attention to immune therapies, anticoagulant drugs, antiplatelet drugs, and analgesics

Medical/aesthetic procedures history will be statistically described by system organ classes (SOC) and preferred terms (PTs) for groups in the FAS by groups (i.e., Group A, Group B and the repeat-treatment subgroup), and be listed for subjects in the SAF.

